# 6.5 Concomitant Therapy

Medications or vaccinations specifically prohibited in the exclusion criteria are not allowed during time periods specified by this protocol for that medication. If there is a clinical

MK-5592-104-04 FINAL PROTOCOL

51

indication for any medications or vaccinations specifically prohibited, discontinuation from study intervention may be required. The investigator should discuss any questions regarding this with the Sponsor Clinical Director. The final decision on any supportive therapy or vaccination rests with the investigator and/or the participant's primary physician. However, the decision to continue the participant on study intervention requires the mutual agreement of the investigator, the Sponsor, and the participant.

Medications prohibited during study treatment are presented in Table 4.

## Table 4 Prohibited Medications During Study Treatment

Prohibited Medications During Study Treatment	Time Period a
Any investigational drug (new chemical or biological entities): Investigational use of approved products or chemotherapy regimens may be permitted with the approval of the Sponsor's Clinical Director before use.	Prohibited during study treatment
Systemic antifungals other than echinocandins (oral, intravenous, or inhaled) as outlined below	Prohibited during study treatment
Echinocandin antifungals (caspofungin, anidulafungin, micafungin)	Prohibited during study treatment except when given for the treatment of invasive candidiasis for a maximum duration of 14 days
Astemizole	Prohibited during study treatment
Cisapride, ebastine, halofantrine, pimozide, quinidine, and terfenadine	Prohibited during study treatment
Ergot alkaloids (ergotamine, dihydroergotamine, or other members of this class)	Prohibited during study treatment
Disopyramide	Prohibited during study treatment
Bepridil	Prohibited during study treatment
Ibutilide	Prohibited during study treatment
Haloperidol	Prohibited during study treatment
Barbiturates, carbamazepine, cimetidine, isoniazid, phenytoin, rifabutin, rifampin, and St. John's Wort ( Hypericum perforatum )	Prohibited during study treatment
HMG-CoA reductase inhibitors metabolized via CYP3A4 (eg, simvastatin, lovastatin, and atorvastatin)	Prohibited during study treatment
Atazanavir, efavirenz, fosamprenavir, or ritonavir	Prohibited during study treatment
Venetoclax	Prohibited during study treatment

Abbreviations: CYP = cytochrome P450; HMG-CoA=beta-hydroxy-beta-methylglutaryl-CoA.

a Medications prohibited during study treatment should not be given during study treatment and for 7 days following the cessation of study treatment. Any deviations to this time period must be discussed with the study team/clinical monitor before initiating any concomitant therapies listed above.

All medications not listed in Table 4 are permitted in the study. Specific medications that are allowed with caution and/or monitoring are presented in Section 6.5.1.

The following topical nonabsorbable antifungals may be used for the treatment of oropharyngeal candidiasis, vaginal candidiasis, or cutaneous fungal infection: oral amphotericin B, miconazole (oral or topical), nystatin (oral or topical), and clotrimazole (oral or topical). All other antifungal therapies must be approved by the Sponsor before use.

# 6.5.1 Medications Allowed With Caution and Clinical Monitoring

Clinical and/or QTc monitoring is recommended when the study treatment is coadministered with one of the following drugs that have reported a potential risk of torsades de pointes:

- Antiarrhythmics (amiodarone, dofetilide, procainamide, sotalol)
- Chlorpromazine
- Clarithromycin
- Domperidone
- Droperidol
- Levomethadyl
- Mesoridazine
- Methadone
- Erythromycin
- Sparfloxacin
- Thioridazine

Medications that are allowed with caution and/or monitoring are presented in Table 5. These drugs are permitted, although their efficacy and safety should be clinically monitored and/or serum levels followed with appropriate dosage adjustments as necessary at the initiation of study treatment, periodically during treatment, and after discontinuation of study treatment.

Medication Class	Medication Name a	Recommendation
Anticoagulants	Coumadin-type	Coumadin-type anticoagulants are permitted, although their efficacy and safety should be clinically monitored and/or serum levels followed with appropriate dosage adjustments as necessary at the initiation of study treatment, periodically during treatment, and after discontinuation of study treatment.
Antiretroviral Therapy	Multiple	As HIV protease inhibitors and NNRTIs are CYP3A4 substrates, it is expected that POS will increase plasma levels of these antiretroviral agents. Participants should be carefully monitored for any occurrence of toxicity during the coadministration of POS and these agents. NOTE: Coadministration of POS with atazanavir, efavirenz, fosamprenavir, or ritonavir is not permitted during the treatment phase of the study.
Benzodiazepines	Alprazolam Midazolam Triazolam	POS 200 mg orally once daily increased the AUC of midazolam by 83% following IV administration. Due to the inhibition of intestinal CYP3A4 by POS, an even greater effect of POS on the AUC of midazolam is expected following oral administration. Dose adjustments should be considered for all benzodiazepines that are metabolized through CYP3A4. POS interferes with the hepatic clearance of triazolam and midazolam, and thus, may enhance the sedative effects of these agents. Therefore, these agents should not be used unless monitoring is provided for excessive sedation
Calcium Channel Blockers	Diltiazem Nifedipine Nisoldipine Verapamil	For calcium channel blockers metabolized through CYP3A4 (eg, diltiazem, nifedipine, nisoldipine, verapamil), frequent monitoring for AEs and toxicity related to calcium channel blockers is recommended during coadministration with POS. Dose adjustment of calcium channel blockers may be required.
Cardiac Glycosides	Digoxin	Administration of other azoles has been associated with increases in digoxin levels. Digoxin levels should be monitored when initiating or discontinuing POS treatment.

Table 5Additional Medications Allowed During the Study That Require Monitoringand/or Dose Adjustment

Medication Class	Medication Name a	Recommendation
Antineoplastic/ Immunosuppressive	Cyclophosphamide	Periodic blood work should be obtained to monitor complete blood count as well as the function of other organs (such as kidneys and liver). Toxicity monitoring to include monitoring for potential myelosuppression, bone marrow failure, urinary tract and renal toxicity, cardiotoxicity including myocarditis, congestive heart failure, and arrhythmia, and pulmonary toxicity. Close monitoring for potential toxicity should occur during coadministration.
Antineoplastic	Trisenox	Prior to initiating therapy with Trisenox, a 12-lead ECG should be performed, and serum electrolytes (potassium, calcium, and magnesium) and creatinine should be assessed. Pre-existing electrolyte abnormalities should be corrected and, if possible, drugs that are known to prolong the QT interval should be discontinued. If it is not possible to discontinue the interacting drug, perform cardiac monitoring frequently. Monitor ECG weekly, and more frequently for clinically unstable patients.
Chemotherapeutic Agents	Anthracycline- based chemotherapeutics	During coadministration, close monitoring for potential cardiotoxicity and hepatotoxicity should occur.
Chemotherapeutic Agents	Vinca alkaloids (eg, vincristine and vinblastine)	Concomitant administration of azole antifungals, including POS, may increase the plasma concentrations of vinca alkaloids, which may lead to neurotoxicity and other serious adverse reactions. Reserve azole antifungals, including POS, for patients receiving a vinca alkaloid, including vincristine, who have no alternative antifungal treatment options.
Immunosuppressive	Sirolimus	Concomitant administration of POS with sirolimus increases the sirolimus blood concentrations by approximately 9-fold and can result in sirolimus toxicity. Monitoring of sirolimus blood levels should be performed on initiation, during coadministration, and on discontinuation of POS treatment, with adjustment of sirolimus doses as necessary.
Immunosuppressive	Cyclosporine	In heart transplant, patients on stable doses of cyclosporine, POS 200 mg QD increased cyclosporine concentrations requiring dose reductions of up to 29%. Cases of elevated cyclosporine concentrations resulting in SAEs, including nephrotoxicity were reported in clinical efficacy studies. Monitoring of cyclosporine blood levels should be performed on initiation, during coadministration, and on discontinuation of POS treatment, with adjustment of cyclosporine doses as necessary.

Medication Class	Medication Name a	Recommendation
Immunosuppressive	Tacrolimus	POS increased Cmax and AUC of tacrolimus (0.05 mg/kg body weight single-dose) by 121% and 358%, respectively. Clinically significant interactions resulting in hospitalization and/or POS discontinuation were reported in clinical efficacy studies. When initiating POS treatment in participants already receiving tacrolimus, the dose of tacrolimus dose should be reduced (eg, to about one-third of the current dose). Thereafter, blood levels of tacrolimus should be monitored carefully during coadministration, and on discontinuation of POS, and the dose of tacrolimus should be adjusted as necessary.
Oral Hypoglycemic Agents/Sulfonylureas	Glipizide	Glucose concentrations decreased in some healthy participants when glipizide was coadministered with POS. Monitoring of glucose concentrations is recommended in diabetic participants.
Tyrosine kinase inhibitors	Ibrutinib	During coadministration with POS, dose adjustment of ibrutinib per product label should occur. Interruption of ibrutinib dose/dose modification for Grade 3 or greater hematologic toxicity is recommended.
Xanthine Derivatives	Theophylline	Theophylline is permitted, although its efficacy and safety should be clinically monitored and/or serum levels followed with appropriate dosage adjustments as necessary at the initiation of study treatment, periodically during treatment, and after discontinuation of study treatment.

Abbreviations: AUC=area under the concentration-time curve; Cmax=observed maximal concentration; CYP=cytochrome P450; ECG=electrocardiogram; HIV=human immunodeficiency virus; IV=intravenous; NNRTI=non-nucleoside reverse transcriptase inhibitor; POS=posaconazole; QD=once daily; SAE=serious adverse event.

a Not all medications from a specific medication class are necessarily listed here.

#### 6.5.2 **Rescue Medications and Supportive Care**

No rescue or supportive medications are specified for use in this study.

# 6.6 **Dose Modification (Escalation/Titration/Other)**

No dose modifications are planned in this study.

#### 6.7 Intervention After the End of the Study

There is no study-specified treatment following the end of the study. Following the completion of study treatment, study participants may continue to receive additional non-study antifungal treatment for the episode of IA or as secondary antifungal prophylaxis as clinically indicated.

#### 6.8 Clinical Supplies Disclosure

This study is open-label; therefore, the participant, the study site personnel, the Sponsor and/or designee are not blinded. Study treatment (name, strength or potency) is included in the label text; random code/disclosure envelopes or lists are not provided.

# 7 DISCONTINUATION OF STUDY INTERVENTION AND PARTICIPANT WITHDRAWAL

### 7.1 Discontinuation of Study Intervention

Discontinuation of study intervention does not represent withdrawal from the study.

As certain data on clinical events beyond study intervention discontinuation may be important to the study, they must be collected through the participant's last scheduled followup, even if the participant has discontinued study intervention. Therefore, all participants who discontinue study intervention before completion of the protocol-specified treatment period will still continue to participate in the study as specified in Section 1.3 and Section 8.9.2.3.

Participants may discontinue study intervention at any time for any reason or be discontinued from the study intervention at the discretion of the investigator should any untoward effect occur. In addition, a participant may be discontinued from study intervention by the investigator or the Sponsor if study intervention is inappropriate, the study plan is violated, or for administrative and/or other safety reasons. Specific details regarding procedures to be performed at study intervention discontinuation are provided in Section 8.1.9 and Section 8.9.2.3.

A participant must be discontinued from study intervention but continue to be monitored in the study for any of the following reasons:

- The participant or participant's legally acceptable representative requests to discontinue study intervention.
- The participant has a medical condition or personal circumstance, which, in the opinion of the investigator and/or Sponsor, placed the participant at unnecessary risk from continued administration of study intervention.
- The participant has a confirmed positive pregnancy test.
- Serious adverse experience related to study therapy or the occurrence of an adverse experience (clinical or laboratory) that, in the judgment of the investigator, warrants withdrawal of study therapy.
- If the QTc interval is >500 msec (based on either Fridericia or Bazett's correction), study therapy may be interrupted for up to 3 days with concomitant monitoring and correction of electrolytes. Study therapy may be resumed if QTc interval decreases to <500 msec.

• If during study treatment the participant has AST or ALT ≥3 × ULN and bilirubin ≥2 × ULN and alkaline phosphatase <2 × ULN, then study therapy may be interrupted for up to 3 days with repeat monitoring of liver function testing. Study therapy may be resumed if repeated liver function testing parameters no longer meet the criteria outlined above and the change is unrelated to study intervention based on the opinion of the investigator. Study therapy should be permanently discontinued if liver function testing continues to exceed the specified parameters with repeat testing regardless of relationship to study medication.

For participants who are discontinued from study intervention but continue to be monitored in the study, all visits and procedures, as outlined in the SoA, should be completed.

See Section 10.7, Appendix 7 for country-specific discontinuation of study intervention requirements.

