# 6.4 Study Intervention Compliance

The volume of injection and the number of tablets/sachets remaining in study packaging will be counted, reviewed, and recorded at regular intervals to monitor treatment compliance.

The shifting of the timing of a dose (within the window provided in Section 8.1.8 to accommodate a participant's schedule) is not considered an interruption.

Interruptions from the protocol-specified treatment plan for  $\geq$ 7 days require consultation between the investigator and the Sponsor and written documentation of the collaborative decision on participant management.

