#### 8.3.3 **Electrocardiograms**

- Single 12-lead ECG will be obtained as outlined in the SoA using an ECG machine that automatically calculates the heart rate and measures PR, QRS, QT, and QTc intervals. Any clinically significant abnormality on study treatment must be followed until stabilization or return to baseline. Refer to Section 7.1 for QTc withdrawal criteria and additional QTc readings that may be necessary.
- For small participants whose size does not allow for a standard 12-lead ECG, a modified 12-lead ECG may be obtained.

Note: When the collection of vital signs, ECGs, and PK samples coincide, the blood samples for PK determination should be collected first (so that the PK samples are collected on time), followed by the vital signs, and then the ECG. It is preferred that the ECG be performed at the same time each day (eg, morning) to reduce diurnal variation.

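### Section 7.1 lists QTc above 500 msec as a mandatory reason to discontinue, but the bullet only permits interruption and does not say what follows if QTc has not fallen below 500 msec

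*Combined protocol and SAP*

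**What the plan says.** Section 7.1 opens its list with "A participant must be discontinued from study intervention but continue to be monitored in the study for any of the following reasons". The QTc entry in that list is triggered by a value above 500 msec under either the Fridericia or the Bazett correction. Its action is that "study therapy may be interrupted for up to 3 days with concomitant monitoring and correction of electrolytes", followed by "Study therapy may be resumed if QTc interval decreases to <500 msec". The entry ends there.

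The next entry, on liver tests, sits under the same lead-in. It too allows an interruption of up to 3 days and a conditional resumption, but it goes on to cover the persistent case: "Study therapy should be permanently discontinued if liver function testing continues to exceed the specified parameters with repeat testing".

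Section 8.3.3 (Electrocardiograms) contains no rule of its own. It says: "Refer to Section 7.1 for QTc withdrawal criteria and additional QTc readings that may be necessary".

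**The concern.** The lead-in makes discontinuation compulsory for every listed reason. The QTc entry makes interruption optional and resumption possible. A site that follows the lead-in stops treatment for good. A site that follows the bullet may pause and restart. Where the bullet's resumption condition is not met, the site has no written instruction specific to QTc.

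Section 2.3 names QTc prolongation as an identified risk of posaconazole, and Section 6.5.1 allows several drugs with a reported torsades risk, with monitoring recommended. Safety is the primary objective. A numeric safety threshold should lead to one stated action that every site can read the same way. There is a smaller reporting consequence: the same QTc event could be recorded as an interruption or as a discontinuation.

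**Working it through.** No arithmetic applies, because the documents attach no rate or expected count to on-treatment QTc events. The check is to follow each course after a QTc above 500 msec through the lead-in and the bullet.

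| Course after a QTc above 500 msec | Lead-in of 7.1 | QTc bullet of 7.1 |
|---|---|---|
| Interrupted; QTc below 500 within 3 days | Discontinue | May resume |
| Interrupted; QTc still above 500 after 3 days | Discontinue | Silent |
| Interrupted; QTc exactly 500 | Discontinue, since the reason arose | Silent: the trigger needs a value above 500 and resumption needs one below |
| Not interrupted | Discontinue | Left open by the permissive verb; no outcome stated |

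The first row is a direct conflict. In the other three, the lead-in gives an answer only if it is read literally, and a literal reading would also remove the permission to interrupt and resume.

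**Does another section settle it?**
- Section 8.3.3 points back to Section 7.1, both for the criteria and for additional readings. Section 7.1 mentions monitoring during the interruption but sets no schedule of repeat readings.
- Section 6.4 says that interruptions of 7 days or more "require consultation between the investigator and the Sponsor and written documentation of the collaborative decision on participant management". That is a general rule, and its threshold lies beyond the 3-day limit.
- Exclusion criterion 11 in Section 5.2 uses the 500 msec threshold at screening only.
- Sections 8.1.9 and 8.9.2.3 describe procedures after discontinuation, not when to discontinue.
- Appendix 7, to which Section 7.1 refers for country requirements, has an ECG schedule for Italy and eligibility and diagnostic items for South Korea. It has no QTc stopping rule.

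**The liver entry.** It shares the conflict between lead-in and bullet, but it states what follows if the abnormality persists. The QTc entry has no matching sentence.

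**Which analyses depend on stopping rather than pausing?**
- *Primary endpoint (9.4.2):* the proportion with at least one treatment-related AE in the treatment period plus 14 days. An event counts whether therapy is then paused or stopped.
- *Full Analysis Set (9.5.1):* membership turns on IA classification, at least one dose, a post-allocation observation and, where needed, baseline data. Pausing or stopping does not by itself remove anyone.
- *Discontinuations due to AE (9.6.3, Table 8):* this can change, but it is a descriptive item with no confidence interval.
- *Timing of the EOT visit (8.9.2.3) and of the response assessment (8.2.1):* stopping early brings both forward.
- *Responder Population (9.5.1):* it could change only indirectly, through response status at the end of treatment.

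**The case against.** The strongest answer is that the text reads naturally as a default with an exception. Discontinuation is the default. A pause of up to 3 days is allowed first, and resumption depends on QTc falling below 500 msec. If it does not fall, the exception lapses and the lead-in governs. Section 8.3.3 supports this by treating Section 7.1 as the home of the withdrawal criteria, and the liver entry follows the same pattern. Two other entries, on unnecessary risk and on adverse experiences that warrant withdrawal, also apply to a participant with persistent prolongation. Exposure to the ambiguity is limited too: QTc above 500 msec at screening is excluded, as is a known history of torsade or QT prolongation under exclusion criterion 4. Outside Italy, the scheduled on-treatment ECGs after Day 1 are at Day 3, Week 1, Week 12 and EOT.

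Much of this stands. The default-with-exception reading is plausible, so it would be too strong to infer that the protocol authorizes continued dosing above 500 msec or leaves sites with no guidance at all. But that reading is not written down. It does not explain why the interruption is itself optional, and it leaves a value of exactly 500 msec unassigned. The judgment-based entries do not turn a numeric threshold into a uniform rule.

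A reader might also infer that the response-rate denominator or the primary endpoint is at risk. The definitions in Sections 9.5.1 and 9.4.2 do not support that. Nor do the documents show that sites will in fact act differently; they show only that the text allows it.

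**Conclusion.** The inconsistency is real and should be corrected. Section 7.1 places a permissive, reversible action under a compulsory lead-in. For QTc it states no explicit outcome when the resumption condition is not met or when therapy is not interrupted. The case for change rests mainly on safety clarity. The secondary effects are confined to the descriptive count of discontinuations due to adverse events, the timing of end-of-treatment assessments and, indirectly, responder status.

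The size cannot be calculated. With about 30 participants expected in the safety population (Section 9.9.2), one participant weighs 1/30 = 3.3 percentage points. That holds for any single event and says nothing about how often this one will occur, so it should not be read as an estimate of the effect.

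The conclusion rests on the wording of the protocol alone. The Investigator Study File Binder and the DMC charter are not among the documents and might add operational detail. Section 8.3.3 nevertheless names Section 7.1 as the place for the criteria.

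**What to change.** Reconcile the lead-in of Section 7.1 with the QTc and liver entries. Put the reasons that compel discontinuation in one list and the rules for interruption and resumption in another. Have the QTc text say explicitly what follows when the resumption condition is not met, including a value of exactly 500 msec, and when therapy is not interrupted. Then check that the reference in Section 8.3.3, including its mention of additional readings, matches the revised text. The sponsor should set the clinical content; the fact that the liver entry states an outcome is no argument for adopting the same outcome for QTc. The cost is a wording change in one section, with no change to the design, sample size or analysis.

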Serious Adverse Event (SAE)	Report if: - due to protocol- specified intervention - causes exclusion - participant is receiving placebo run-in or other run-in treatment	Report all	Report if: - drug/vaccine related. (Follow ongoing to outcome)	Within 24 hours of learning of event
Pregnancy/Lactation Exposure	Report if: - due to intervention - causes exclusion	Report all	Previously reported – Follow to completion/termination; report outcome	Within 24 hours of learning of event
Event of Clinical Interest (require regulatory reporting)	Report if: - due to intervention - causes exclusion	Report - Potential drug- induced liver injury (DILI) - Require regulatory reporting	Not required	Within 24 hours of learning of event
Event of Clinical Interest (do not require regulatory reporting)	Report if: - due to intervention - causes exclusion	Report - non-DILI ECIs and other events not requiring regulatory reporting	Not required	Within 5 calendar days of learning of event
Cancer	Report if: - due to intervention - causes exclusion	Report all	Not required	Within 5 calendar days of learning of event
Overdose	Report if: - receiving placebo run-in or other run-in medication	Report all	Not required	Within 5 calendar days of learning of event

C Confidential

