# 8.4.7 Events of Clinical Interest (ECIs)

Selected nonserious and SAEs are also known as ECIs and must be reported to the Sponsor.

Events of clinical interest for this study include:

1. An elevated AST or ALT lab value that is greater than or equal to 3X the upper limit of normal and an elevated total bilirubin lab value that is greater than or equal to 2X the upper limit of normal and, at the same time, an alkaline phosphatase lab value that is less than 2X the upper limit of normal, as determined by way of protocol-specified laboratory testing or unscheduled laboratory testing.\*

\*Note: This section reflects the handling of nonserious ECI. ECI events meeting SAE criteria are to be reported in the same manner as SAE. The purpose of the criteria is to specify a threshold of abnormal hepatic tests that may require an additional evaluation for an underlying etiology. The study site guidance for assessment and follow-up of these criteria can be found in the Investigator Study File Binder (or equivalent).

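### In Section 7.1 a rise in alkaline phosphatase can meet the laboratory half of the hepatic restart rule while AST/ALT and bilirubin stay above their limits

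*Combined protocol and SAP*

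**What the plan says.** The hepatic item in Section 7.1 has three parts.

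- **Trigger.** The pattern that sets the rule in motion is "AST or ALT ≥3 × ULN and bilirubin ≥2 × ULN and alkaline phosphatase <2 × ULN". For a child who shows it on treatment, the item provides that "study therapy may be interrupted for up to 3 days with repeat monitoring of liver function testing".
- **Restart.** Dosing "may be resumed if repeated liver function testing parameters no longer meet the criteria outlined above and the change is unrelated to study intervention", the second condition being a matter for the investigator's opinion.
- **Permanent stop.** Dosing "should be permanently discontinued if liver function testing continues to exceed the specified parameters with repeat testing regardless of relationship to study medication".

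Section 8.4.7 makes the same three-part pattern an event of clinical interest, described as "a threshold of abnormal hepatic tests that may require an additional evaluation for an underlying etiology". Neither that section, nor the rest of Section 7.1, nor Appendix 7 says that AST/ALT or bilirubin must fall before restart, or how a rise in ALP between the two tests is to be handled.

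**The concern.** The restart test is the negation of the whole trigger, and the trigger's three components do not all point the same way. AST/ALT and bilirubin count when they are high; ALP counts when it is low. The trigger can therefore switch off in two quite different ways: AST/ALT or bilirubin falls, or ALP rises. The first is recovery. The second is not, and the text treats both alike.

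Hepatic toxicity is a named risk of the drug (Section 2.3). A restart rule in a paediatric trial should not be satisfiable by a further liver test becoming abnormal while the two that prompted the interruption remain above their limits. The neighbouring QTc item in Section 7.1 shows the usual form: restart is tied to the interval falling back below 500 msec.

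**Working it through.** No figure in the plan is involved, so the check is an enumeration of the rule as written.

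**Inputs (all from Section 7.1).** On repeat testing let T = AST or ALT ≥3 × ULN, B = bilirubin ≥2 × ULN, P = ALP ≥2 × ULN, and U = change judged unrelated. Each is true or false, giving 2 × 2 × 2 × 2 = 16 outcomes.

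**Rules.**
- Trigger = T and B and not P.
- Restart permitted = not(trigger) and U.

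**Restart count.** U holds in 8 outcomes and the trigger persists in 1 of them, so restart is permitted in 8 − 1 = 7. One of the 7 is T, B, P, U all true: AST/ALT and bilirubin still above their limits, ALP now raised.

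**Illustration (hypothetical values, × ULN).**

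| | ALT | Bilirubin | ALP | Trigger met? |
|---|---|---|---|---|
| First test | 5 | 2.5 | 1.8 | Yes: 5 ≥ 3, 2.5 ≥ 2, 1.8 < 2 |
| Repeat | 6 | 3.0 | 2.1 | No: 2.1 is not < 2 |

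All three values have worsened, yet the laboratory half of the restart rule is now met.

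**The stop sentence.** Its reference to specified parameters can be read in three ways.

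| Reading of the stop | Outcomes stopped | Also permitted to restart |
|---|---|---|
| Full trigger persists (T and B and not P) | 1 × 2 = 2 | 0 |
| AST/ALT and bilirubin both still high (T and B) | 1 × 2 × 2 = 4 | 1 |
| Either still high (T or B) | 3 × 2 × 2 = 12 | 3 × 2 − 1 = 5 |

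The middle reading sits best with the verb used, since a value required to lie below a limit cannot go on exceeding it. The text does not settle the matter.

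**AST and ALT counted separately (32 outcomes).** Three of the four AST/ALT combinations have at least one high. Restart is permitted in 16 − 3 = 13, the middle-reading stop covers 3 × 2 × 2 = 12, and the overlap is 3, all with bilirubin high, ALP raised and an unrelated judgment.

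**After the change to the restart clause.** Restart = not(T and B) and U, which is 3 × 2 = 6 of 16 (10 of 32). The only outcome removed is T, B, P, U all true. Overlap with the stop becomes 0 on the first two readings. On the either-test reading it is 2 × 2 = 4, because one test may still be high.

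**The case against.** A reader might infer that Section 7.1 flatly contradicts itself for this child, with one sentence permitting restart and the next ordering a permanent stop. The documents do not support that. If the stop sentence refers back to the full trigger, the two sentences are complements and never overlap. If it means AST/ALT and bilirubin both still high, a permission meets a directive that applies whatever the causality, and the investigator complies with both by stopping. The single conflicting outcome also depends on the reading: the either-test reading gives five.

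It can also be said that low ALP is part of the hepatic pattern throughout the protocol. It appears in the trigger, in the event of clinical interest (8.4.7) and in exclusion criterion 12 (5.2), which applies only with normal ALP. That is a fair reason not to impose a mandatory permanent stop irrespective of ALP, and none is proposed here. It does not justify letting a rise in ALP clear a child to restart.

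Lastly, there are safeguards. Restart needs an unrelated judgment. Section 7.1 separately requires discontinuation for a condition that, "in the opinion of the investigator and/or Sponsor, placed the participant at unnecessary risk from continued administration of study intervention", and for a laboratory adverse experience the investigator thinks warrants it. Potential drug-induced liver injury is reportable within 24 hours (Table 7). Section 8.4.7 refers to site guidance in the study file binder, which is not available here. These make a wrong restart unlikely, but they work by discretion and leave the written test as it is.

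**Conclusion.** The restart clause is wrong as written, and the defect is minor. On every reading of the stop sentence, a rise in ALP to 2 × ULN or more satisfies the laboratory half of the restart test with AST/ALT and bilirubin unimproved or worse, and with an unrelated judgment restart is permitted. This follows from the logic of the rule and needs no assumption. What the stop sentence then requires is unresolved: no stop on the full-trigger reading, a stop on the other two.

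The size is one of 16 logical outcomes (3 of 32 with AST and ALT separate). These are not frequencies, and the number of children affected cannot be derived from the documents. Nor do the documents support inferring an effect on the safety analysis or on event reporting: the event of clinical interest has its own definition, and no analysis uses the restart rule.

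**What to change.** Reword the restart clause in Section 7.1: therapy may be resumed only if, on repeat testing, AST and ALT are both below 3 × ULN or bilirubin is below 2 × ULN, irrespective of any rise in ALP, and the investigator judges the change unrelated.

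In the same amendment, have the sponsor state which tests the stop sentence refers to. The answer affects the restart clause:

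- **Both still high:** the wording above fits, with no overlap.
- **Either still high:** restart should require AST and ALT below 3 × ULN and bilirubin below 2 × ULN (2 of 16 outcomes, no overlap). Otherwise the new clause would loosen the stop.
- **Full trigger:** the outcome removed from restart is then covered by neither sentence and falls to the discretionary stops in Section 7.1.

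The cost is one clause and one clarification at the next amendment, with no new tests or visits. The main downside is that a child whose ALP rises while AST/ALT and bilirubin stay above their limits can no longer restart under this rule, even if the investigator is confident of another cause. The interruption trigger stays ALP-dependent, so a child who first presents with ALP at or above 2 × ULN is still managed by judgment.
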